11.2.2 TREATMENT DISCONTINUATION

Patients will be discontinued from the study treatment if any of the following occurs as noted in Section [9.5](#).

- Disease progression based on RECISTv1.1
- An inter-concurrent illness that prevents further administration of NOX66
- An adverse event that is intolerable to continue the treatment with NOX66 and doxorubicin or any DLT (Section [8.3](#)) that has not resolved to Grade 1.
- Any other reason the Investigator considered that impacts the patient's safety.

For the patients who discontinue treatment, they will continue on study for follow-up visits for tumor evaluation. All anti-cancer treatments should be recorded in the eCRF. In those patients who have evidence of disease progression during the combination of NOX66 and doxorubicin, additional tumor evaluation assessments are not needed.

If a patient is withdrawn from the study at any time, either at his/her request or at the Investigator's discretion, regardless of the reason, the Investigator will record on the relevant page of the eCRF the reason(s) for withdrawal and the day of last dosing. The eCRF (and the clinical study report) will include reasons for patient withdrawals, as well as other details relevant to the patient's withdrawal.

Any patient who appears to be noncompliant from Cycles 2 to 6 should be counselled but not withdrawn from the study. Patients who discontinue for non-safety related reasons or for noncompliance prior to the end of Cycle 1 in the Dose-Escalation Part can be replaced.

Should any patient withdraw or be withdrawn from the study prior to the completion of the Month 18 follow-up visit, every effort should be made to complete the assessments at the End of Study (Section [11.6.2.12](#)). Patients experiencing adverse events should be followed until the AE has resolved, stabilized, or is no longer deemed clinically significant, as judged by the Investigator. Appropriate supportive and/or definitive therapy will be administered as required.

Discontinuation due to treatment failure, as defined by disease progression, is to be expected since doxorubicin is not curative for sarcoma and the optimal dose and dose frequency is not known for NOX66. Alternate treatments for sarcoma may be offered to the patient.

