11.3 STUDY PROCEDURES

[figure not shown]
This study will be conducted in three parts each with screening, treatment and follow up periods as outlined in [Table 2](#). In the Dose Escalation Part, patients receive NOX66 monotherapy followed by NOX66 and doxorubicin combination therapy. In the Dose Expansion Part, patients receive NOX66 and doxorubicin combination therapy only. Patients in each part will be followed post therapy for about 14 months. An overview of phases of the study by period is shown below ([Table 2](#) and [Figure 1](#)).

Table 2 Treatment Periods

	Dose Escalation Only		Dose Escalation & Dose Expansion								
Screening	Monotherapy	Washout	Combination Treatment Cycles [#] 6 Cycles X 21 Days	Follow-Up from C1D1					Month 18 EOS (18 M from C1D1)		
				Month 6 (6 M from C1D1)	Month 9 (9 M from C1D1)	Month 12 (12 M from C1D1)	Month 15 (15 M from C1D1)				
28 days	7 days	5 days	126 days	1.8 M from C6D21	3 M from last f/u	3 M from last f/u	3 M from last f/u	3 M from last f/u			
	12 days		4.2 Months	1.8 Months	3 Months	3 Months	3 Months	3 Months			
1.3 Months			18 Months								
~ 20 Months											

C1D1 = Cycle 1 Day 1; EOS = End of Study; f/u = follow-up, M = month

[#]Each combination therapy cycle is 21 days with NOX66 administered on Days 1-7 at a fixed dose and regimen. On Day 2 doxorubicin is administered intravenously for 15 minutes at 75 mg/m². No treatment is administered on Days 8-21. During the follow-up period, neither NOX66 or doxorubicin is administered, but other approved or investigational medication for sarcoma may be administered.

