11.4.4 EFFICACY

Treatment responses

Computer Tomography or MRI will be performed at Screening, prior to the start of Cycles 1 (only in the Dose Escalation cohorts if the previous scan was done more than 28 days previously), at the end of Cycles 2, 4, and 6, at 6, 9 and 12 months after the start of the combination therapy and at the End of Study (Month 18) or at Early Termination (ET) if the patient discontinues from the trial. Changes in the size and number of target lesions will be evaluated using RECIST v1.1 criteria, compared to baseline (Screening) or prior to Cycle 1 scan whichever is appropriate.

Other Outcome Measures

Each patient's ECOG Performance status will be assessed at the end of NOX66 monotherapy, at the start of Cycle 5 and at End of Study, compared to baseline. Assessments of pain, fatigue and QOL will be made at the end of NOX66 monotherapy (fatigue and pain only), on Day 1 of each cycle for the combination of NOX66 and doxorubicin, at Months 6, 9 and 12 of the follow-up period and at the End of Study, compared to baseline. Assessments of acceptance of suppository administration will be made at the end of NOX66 monotherapy and on Day 1 of each cycle for the combination of NOX66 and doxorubicin.

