11.6.2.12 Month 18 (from Cycle 1 Day 1) - End of Study/Early Termination

- Assess tumor response with CT or MRI, including patients who discontinue the study for progressive disease.
- Measure vital signs (blood pressure, pulse [radial or brachial (to be measured over 30 seconds if performed manually)], respiration rate and body temperature [oral or aural]; Section 11.4.2.1).
- Assess ECOG performance status.
- Collect urine and fasting blood samples for clinical laboratory tests (Section 11.4.2.4).
- Administer questionnaires BPI-SF, EORTC QLQ-C30 and EORTC QLQ-FA12.
- Perform a physical examination (Section 11.4.2.2).
- Review and record concomitant medications.
- Assess and review TEAEs (Section 16).
- Assess overall survival.

Table 4 Schedule of Procedures and Assessments for Three Periods of the Study

Procedure/Assessment	Study Day	Dose Escalation & Dose Expansion	Dose Escalation NOX66 Monotherapy Period							
		Screening	Monotherapy (Days)							Off-treatment Days
		Day -28 to Day -1	1	2	3	4	5	6	7	8
Obtain informed consent		X								
Inclusion/exclusion criteria		X	X							
Medical and surgical history ¹ (including histopathology data and STS grade)		X	X							
Assess disease status (CT and/or MRI) ²		X								X
Vital signs ³		X	X						X	
Physical examination ⁴		X	X						X	
ECOG performance status		X							X	
Hematology, clinical chemistry ⁵		X	X						X	
Urine pregnancy test (WOCBP only)		X	X							
BNP, troponin I			X						X	
Blood for cytokines, chemokines, immunoassays (ENOX2)		X [†]	X [†]						X	
Genetic mutation sample		X [†]	X [†]							
Archival tissue sample (Optional)		X								
Urinalysis		X	X						X	
12-lead ECG ⁶		X	X						X	
Holter monitoring ⁶									X	
Dispense 7-day supply of NOX66			X							
Echocardiography		X								
Administer NOX66 ⁷			X	X	X	X	X	X		
PK samples ⁸			X	X					X	X
Record AEs		X						X		
Prior & concomitant medications		X						X		
Assess dosing compliance ⁹									X	
Brief Pain Inventory (BPI-SF) ¹⁰			X						X	
EORTC QLQ-C30 ¹⁰			X							
EORTC QLQ-FA12 ¹⁰			X						X	
Suppository Acceptance Questionnaire ^{10, 19}								X		

Procedure/Assessment Study Day	Dose Escalation and Dose Expansion Combination of Doxorubicin and NOX66 Treatment Period Cycles 1 - 3																
	Cycle 1 ¹						Cycle 2					Cycle 3					
	1	2	3-7	8	9 & 16	21	1	2	3-7	9 & 16	21	1	2	3-7	8	9 & 16	21
Assess disease status (CT and/or MRI) ²											X						
Vital signs		X						X					X				
Physical examination	X						X					X					

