11. The additional tests for hematology and serum chemistry on Days 9 and 16 are to assess any hematological or clinical laboratory tests for DLTs and/or require a dose reduction to 60 mg/m^2 or lower (37.5 mg/m^2 or 18.75 mg/m^2 based on serum bilirubin), or a delay in initiation of another cycle of the combination. These additional hematological and clinical laboratory tests should be performed at each cycle. Visit windows are ± 2 days of the scheduled visit.
12. During combination treatment cycles, NOX66 is administered on Days 1 to 7 and doxorubicin is administered on Day 2.
13. Doxorubicin (75 mg/m^2 or reduced dose) to be given on Day 2 of each 21-day cycle.
14. For Dose-Escalation Cohorts, PK samples will be obtained at pre-dose and at 1 and 2 hours post NOX66 on Day 2 Cycle 1. PK samples for idronoxil will be obtained on Day 2 of Cycles 2, 4 and 6 at pre-dose and 4 hours post dose. Additional PK samples for idronoxil will also be obtained pre-dose on Day 7 and at 8 or 12 hours after the last dose of NOX66 on Day 7 for those on a TID or BID regimens, respectively on Cycles 1, 3, and 5. For the Dose Expansion Cohort, PK samples for idronoxil will be obtained on Day 2 of Cycles 1, 2, 4, and 6 at pre-dose and at 4 hours post NOX66 and on Cycle 1 at 6 hours post NOX66. On Cycles 1, 3, and 5 PK samples are to be collected just prior to the morning dose of NOX66 on Day 7. For doxorubicin in the Dose Escalation Cohort, PK samples will be obtained at 0.5, 4 and 6 hours after the end of infusion on Day 2 Cycle 1 and at 0.5 and 4 hours at the end of infusion on Day 2, Cycles 2, 4 and 6. For doxorubicin in the Dose Expansion Cohort, PK samples will be obtained at 0.5, 4 and 6 hours after the end of infusion on Day 2 Cycle 1 and at 0.5 and 4 hours at the end of infusion on Day 2, Cycles 2, 4 and 6 ([Table 7](#)).
15. All patients who discontinue the study early for whatever reason after the first dose of NOX66, or during treatment cycles (Cycles 1-6), will be followed up within 28 days of discontinuation and submit to assessments detailed in the column of Cycle 6 Day 21/Early Termination. Patients who discontinue the study early during the follow-up period will complete a final visit with assessments detailed in the column of End of Study/Early Termination. Patients who complete the study in full will have an End of Study visit at Month 18.
16. Adverse events to be recorded up to 30 days after the last dose of NOX66 or doxorubicin, whichever is longer.

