14.3.10 EFFICACY ANALYSES

Treatment response will be assessed by RECIST v1.1 criteria for patients in the FAS at the end of Cycles 2, 4, and 6, at the 6-month, 9-month, and 12-month follow-up visits, and at the End of Study or Early Termination. Along with CR, PR and SD, the ORR will be defined as the relative frequency of patients with either CR or PR, and the DCR will be defined as the relative frequency of patients with CR, PR, or SD.

The ORR, the DCR, and the frequencies of CR, PR, SD, and PD will be summarized at the end of Cycles 2, 4 and 6 and at the 6-month, 9-month, 12-month and up to 18-month follow-up visits. A summary will also be provided of best response on study.

At the assessment at the end of Cycle 6, a one-sided exact binomial test will be used to test the null hypothesis that the ORR is no greater than 0.20 (20%) against the alternative hypothesis that the ORR is greater than 0.20 at an approximate level $p = 0.025$. A similar test against the performance level of 0.20 will be performed for the rate of best objective response on study.

Overall survival will be defined as the time in months from initial treatment until death or censoring. Patients not known to have died at the time of analysis will be censored at the time of last contact with study personnel., including patients who are lost to follow-up. The overall survival curve will be estimated for the FAS by the Kaplan-Meier method.

Progression-free survival will be defined as the time in months from initial treatment until death, disease progression, or censoring. Patients who are lost to follow-up will be censored at the time of their last contact with study personnel. Patients who leave the study to begin an alternative therapy will be censored on their day of study discontinuation. The PFS curve will be estimated for the FAS by the Kaplan-Meier method.

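### The test of best objective response on study has no stated end to its response window, so a response to a later sarcoma drug can be counted for the combination; the PFS censoring rules leave a narrower gap

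*Combined protocol and SAP*

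**What the plan says.** Section 14.3.10 tests ORR at the end of Cycle 6 against 0.20 with a one-sided exact binomial test at an approximate level of 0.025. It then adds: "A similar test against the performance level of 0.20 will be performed for the rate of best objective response on study". It also summarises ORR and DCR by visit up to Month 18. No sentence limits which scans count.

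The conduct sections bear on this as follows:

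- Section 11.2.2, after treatment stops: "For the patients who discontinue treatment, they will continue on study for follow-up visits for tumor evaluation".
- Section 11.3, footnote to Table 2: "During the follow-up period, neither NOX66 or doxorubicin is administered, but other approved or investigational medication for sarcoma may be administered".
- Section 9.4 gives only withdrawal of consent and death as reasons for study withdrawal. A new drug is not one.
- Section 11.2.2, on progression: "In those patients who have evidence of disease progression during the combination of NOX66 and doxorubicin, additional tumor evaluation assessments are not needed". The waiver is limited to progression during the combination.
- Section 11.6.2.12, Month 18/Early Termination: "Assess tumor response with CT or MRI, including patients who discontinue the study for progressive disease".
- Table 4, footnote 15: patients who discontinue the study during the treatment cycles "will be followed up within 28 days of discontinuation and submit to assessments detailed in the column of Cycle 6 Day 21/Early Termination".
- Section 11.4.4: lesion change is judged "compared to baseline (Screening) or prior to Cycle 1 scan whichever is appropriate".

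For PFS, Section 14.3.10 censors patients who leave the study for another therapy on the day they discontinue the study, and censors losses to follow-up at last contact. Section 11.6.2.11 (Month 15) collects adverse events and survival only, whereas the Synopsis and Section 8.1.2 say the call or chart review serves both PFS and OS. Section 14.3.12 defers further data-handling rules to a SAP to be approved before the expansion cohort opens. Its text is not in the documents.

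**The concern.** Table 2 ends treatment 4.2 months after Cycle 1 Day 1, and follow-up runs to Month 18. Of the seven scheduled post-baseline response assessments (end of Cycles 2, 4 and 6, Months 6, 9 and 12, End of Study), four fall after treatment has ended, when another sarcoma drug may be in use. Followed as written, the best response on study for such a patient can be a response to that other drug.

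Three things are at stake. A formal test of the combination against 0.20 could include responses it did not produce. Stable disease on a later drug could count as disease control in the Month 6 to 18 summaries. PFS could include time on another drug, or time after the last scan during which progression was not looked for.

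**Working it through.** **The plan's own figure.** Section 14.1 states an 85% probability that the observed rate exceeds 18% when 24% (8/34) is expected. Exact binomial, N=34: P(X≥6) = 0.859 at p = 0.24 and 0.845 at p = 8/34, so 85% reproduces if 6/34 itself counts as success. Read strictly (X≥7), it is 0.741 and 0.720. This does not affect the present point. What matters from Section 14.1 is that the assumed gain is 8 − 6 = 2 patients in 34.

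**Who is exposed.**

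1. Non-responders who start another drug before progressing. They stay on study and on the scan schedule, and nothing excludes their later scans.
2. Patients who progress during follow-up. The Section 11.2.2 waiver does not reach them, so the Month 9, 12 or 18 scans remain scheduled.
3. Patients who progress on the combination. Further scans are waived, an early-termination visit falls within 28 days, and response is judged against the original baseline. They are exposed only through the Month 18/Early Termination scan, where Section 11.6.2.12 conflicts with Section 11.2.2.

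**Test inputs (Section 14.3.10).** Null rate 0.20, one-sided level 0.025. The smallest c with P(X≥c | N, 0.20) ≤ 0.025 is 13 for N=34 (the maximum, Section 14.1), 9 for N=22 (assumed: 16 expansion plus 6 escalation patients at the MTD) and 8 for N=16 (expansion only).

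**Illustration.** Let f be the share of non-responders with a counted later-drug response, that is, the share who start another drug and are still scanned, times that drug's response rate. At a true ORR of 0.20 the counted rate is 0.20 + 0.80f. The documents give no value for f. For example, 20% × 10% = 2%, 50% × 10% = 5% and 50% × 20% = 10%.

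| f | Counted rate | N=34, c=13 | N=22, c=9 | N=16, c=8 |
|---|---|---|---|---|
| 0 | 0.200 | 0.011 | 0.020 | 0.007 |
| 2% | 0.216 | 0.020 | 0.032 | 0.011 |
| 5% | 0.240 | 0.046 | 0.060 | 0.021 |
| 10% | 0.280 | 0.129 | 0.134 | 0.051 |

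At f = 2% the expected number of such patients is 34 × 0.80 × 0.02 = 0.54, and 0.35 and 0.26 at N=22 and N=16. Only N=22 then passes 0.025. If the approximate level admits the next lower cut, the error without any later-drug response is already 0.027 (12 of 34, or 7 of 16), and f = 2% takes it to 0.047 and 0.039.

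**How plausible are 5% and 10%?** Groups 1 and 2 come mainly from non-responders still unprogressed when treatment ends. Section 6.1 cites median PFS of 4.1 and 4.6 months on doxorubicin alone and 6.6 and 7.4 months on combinations. Assume exponential PFS, 20% responders and every responder unprogressed at 4.2 months. Then S = 2^(−4.2/median), and the unprogressed share of non-responders is (S − 0.20)/0.80:

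- median 4.1: S = 0.492, share 36%; median 4.6: S = 0.531, share 41%
- median 6.6: S = 0.643, share 55%; median 7.4: S = 0.675, share 59%

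A 50% share is therefore out of reach at the doxorubicin-alone medians. At the combination medians it needs 0.50/0.593 = 84% to 0.50/0.554 = 90% of those patients to start another drug and be scanned. If all of the 36% did so, f = 5% would still need a later-drug response rate of 0.05/0.3645 = 13.7%. The 5% and 10% rows are upper-end sensitivity values. The two-patient gain in Section 14.1, as a share of 28 non-responders, is 2/28 = 7.1%, which also lies in that upper range.

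**PFS.** The only new-therapy rule applies to patients who leave the study, but Sections 9.4 and 11.2.2 keep most patients on it. A patient who starts another drug unprogressed and stays has no stated rule. Last contact may be the Month 15 call, which as listed involves no scan and no progression question.

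**The case against.** The strongest reply is that the rule is deferred, not refused. Section 14.3.12 promises data-handling rules in a SAP, and a response window is that kind of rule. RECIST v1.1 is also adopted by reference and may limit best response, which cannot be checked here. Both stand as limits: the finding is that no cut-off is stated in these documents, not that none will exist. An unprogressed patient on a new drug would not be caught by a limit at progression in any case.

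Second, the PFS rule can be read as treating a new therapy as departure from the study, which would close the response window too. Sections 9.4, 11.2.2 and 11.3 point the other way, so at best the text is ambiguous.

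Third, counting progression or death regardless of new therapy is a legitimate PFS definition. That is so, but the plan does not state it, and it does not justify censoring at a contact without a scan.

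A reader might also infer that the false-positive rate of this test is about 0.13, or that progressors in general can return as responders. The documents support neither. The first needs f = 10%, for which they give no basis. The second overlooks the scan waiver, the 28-day exit visit and comparison with the original baseline for patients who progress on the combination.

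**Conclusion.** The point holds. As written, best objective response on study can credit the combination with a later drug's response, both in patients who start another drug unprogressed and in those who progress during follow-up. The amount is unknown. With f = 2%, an assumption, the false-positive rate rises by 0.004 to 0.012 depending on N, and exceeds 0.025 at the strict cuts only for N=22. Larger effects need high switching or a high later-drug response rate.

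The consequence is limited. The test is secondary with no decision rule, the end-of-Cycle-6 test is much less exposed because other sarcoma drugs are mentioned for follow-up, and the MTD and DLT decisions are unaffected. The PFS gap is narrower, because one new-therapy rule exists. The change is still worth making, because the efficacy result will be read as belonging to the combination.

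**What to change.** In Section 14.3.10, or in the SAP due before the expansion cohort opens:

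- Count best response, ORR and DCR only from scans up to the earlier of documented progression or start of new anti-cancer therapy. List later scans separately.
- Censor PFS at the last adequate tumour assessment before new therapy or loss to follow-up, whether or not the patient leaves the study. Add one sensitivity analysis counting progression or death regardless of new therapy.
- Reconcile Section 11.2.2 with Section 11.6.2.12 on scans after progression, and Section 11.6.2.11 with the Synopsis and Section 8.1.2 on whether the call or chart review collects progression.

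The analysis rules need no new data, since Section 11.2.2 already requires that "All anti-cancer treatments should be recorded in the eCRF". The cost is slightly fewer counted responses and earlier, possibly informative, PFS censoring in a few patients, which is why the sensitivity analysis is included.

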8.1.2 COHORT EXPANSION

After the dose escalation part is completed, 16 patients will be enrolled into a Dose Expansion Cohort at the MTD of the combination. All patients will enter directly into 21-day combination cycles and will be given NOX66 therapy for 7 days and doxorubicin will be administered on Day 2. This will be followed by a 2-week rest period. Treatments will continue up to 6 cycles.

For both the Dose Escalation and Cohort Expansion groups, treatment will be terminated upon disease progression, unacceptable toxicity or a maximum of 6 cycles. In patients who develop Grade 3 or 4 toxicity determined to be related to NOX66, the Investigator may reduce the dose or frequency of dosing by one level so that the patients can remain in the study. Furthermore, all patients will be actively followed up for about 14 months after completion of Cycle 6 (including scheduled visits every 3 months) followed by telephone follow-up/chart review, for PFS and OS, at 15 and 18 months from the start of Cycle 1.

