11.6.2.11 Months 15 (from Cycle 1 Day 1)

- Conduct telephone follow-up or chart review.
- Assess and review AEs.
- Assess overall survival.

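### PFS for patients lost to follow-up is censored at last contact, not at the last tumour assessment, so missed scans count as progression-free time

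*Combined protocol and SAP*

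**What the plan says.** Section 14.3.10 defines PFS as time from initial treatment to death, progression or censoring, estimated by Kaplan-Meier in the Full Analysis Set. It gives two censoring rules:

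- Lost to follow-up: "Patients who are lost to follow-up will be censored at the time of their last contact with study personnel".
- Alternative therapy: "Patients who leave the study to begin an alternative therapy will be censored on their day of study discontinuation".

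It does not mention the last evaluable tumour assessment. It gives no PFS rule for missed scans or for patients still event-free at the analysis.

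Section 11.4.4 schedules imaging "at the end of Cycles 2, 4, and 6, at 6, 9 and 12 months after the start of the combination therapy", and then at Month 18. Section 11.6.2.11 describes Month 15 as "Conduct telephone follow-up or chart review", with adverse events and survival but no imaging; the follow-up part of Table 4 agrees. Section 8.1.2 nevertheless describes "telephone follow-up/chart review, for PFS and OS, at 15 and 18 months from the start of Cycle 1". Section 11.6.2 also encourages telephone contact between visits.

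The late follow-up is described in three ways. The synopsis counts the 15- and 18-month contacts from completion of Cycle 6. Section 8.1.2 counts them from the start of Cycle 1 and makes both telephone or chart review. Section 11.6.2.12 makes Month 18 a visit with imaging: "Assess tumor response with CT or MRI, including patients who discontinue the study for progressive disease".

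**The concern.** A telephone call can show that a patient is alive. It cannot show that RECIST progression has not occurred. If the censoring date is a contact later than one or more missed scans, the patient stays in the Kaplan-Meier risk set at those scan times but cannot contribute an event there. Each step of the curve is then too small.

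The error always favours the treatment. The trial has no control arm (section 6.2), so the doxorubicin medians of 4.1 and 4.6 months in section 6.1 are the context a reader has for the PFS result. Because this is a stated rule and not an omission, an SAP that follows the protocol would inherit it.

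**Working it through.** The plan gives no PFS target, event count or dropout rate, so there is no stated figure to reproduce. The check asks when the rule changes the curve, and by how much.

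**Inputs from the documents.** Cycles last 21 days. With 30.44 days per month, the scans at the end of Cycles 2, 4 and 6 (days 42, 84 and 126) fall at 1.38, 2.76 and 4.14 months. Later scans are at Months 6, 9, 12 and 18. Illustrative true medians are 4.6 and 4.1 months (section 6.1).

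**Assumptions, not in the documents.** PFS is exponential. 10, 20 or 30% of patients stop scans after Cycle 2, 4 or 6 (equally likely), independently of their disease course. Contact then lasts 3 months, 6 months, or to a time spread over Months 9-15.

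**One step by hand.** With a median of 4.6 months, the hazard is ln 2 / 4.6 = 0.1507 per month. The chance of progressing between two scans 1.38 months apart is 1 - exp(-0.1507 × 1.38) = 0.188. Suppose 30% stop scans, a third of them after Cycle 2. Then 10% of those at risk at the Cycle 4 scan are unscanned but still in contact, and the observed drop is 0.188 × 0.90 = 0.169. PFS at that scan reads 0.812 × 0.831 = 0.675, where full scanning gives 0.812 × 0.812 = 0.660. That is 1.5 points after one missed scan, and it accumulates over later scans.

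**Whole curve.** Kaplan-Meier on 400,000 simulated patients, true median 4.6 months. The full-scan value at 12 months is 0.5^(12/4.6) = 16.4%. Censoring at the last scan returned 16.3-16.5% in every case.

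| Contact after last scan | 10% stop | 20% stop | 30% stop | 12-month overstatement |
|---|---|---|---|---|
| 3 months | 17.1% | 17.7% | 18.5% | about 1-2 points |
| 6 months | 17.9% | 19.6% | 21.4% | about 2-5 points |
| to Months 9-15 | 20.4% | 24.8% | 29.3% | about 4-13 points |

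A second model, in which scans stop at a random time (10-30% of patients by Month 12) and contact lasts 3 or 6 months more, overstates 12-month PFS by 0.9 to 6.7 points across medians of 4.1, 4.6 and 7.4 months.

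**Median.** The curve steps only at scan dates. With a true median of 4.6 months, full-scan PFS is 53.6% at 4.14 months and 40.5% at Month 6, so the estimated median is 6.0 months under both rules in every scenario in the table. With a true median of 4.1 months, full-scan PFS at 4.14 months is 0.5^(4.14/4.1) = 49.7%, just under one half. The estimate is then 4.1 months with last-scan censoring and 6.0 months with last-contact censoring.

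**When there is no effect.** If a patient is scanned at Month 12, telephoned at Month 15 and then lost, no scheduled scan falls between the two candidate censoring dates. No event can be detected there, and PFS at Months 6, 9, 12 and 18 is identical under both rules. The same holds whenever contact ends before the next scheduled scan.

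**The case against.** **The protocol works against long unscanned contact.** Section 11.2.2 keeps patients who stop treatment on study for tumour evaluation. Table 4 bars a new cycle until scheduled imaging has ruled out progression, and requires assessment of early discontinuers within 28 days. This stands as a reason to expect the lower part of the range. It does not make the rule right for patients who do miss scans.

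**The rule is narrow and the endpoint secondary.** The last-contact sentence covers only patients lost to follow-up. PFS has no test, target or power, and no comparison of PFS with historical data is planned. This stands, and it limits the severity.

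**An SAP is still to come.** Section 14.3.12 promises further data-handling rules, and section 17.3 allows changes to the planned analysis to be documented there. The SAP could carry the correction, but it would have to replace the stated rule, not only add detail to it.

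**Two stronger readings do not hold.** A reader might infer that each patient telephoned at Month 15 after a Month 12 scan inflates PFS by three months; as shown above, the curve does not change. A reader might also infer that OS is biased downward, because section 14.3.10 says "Patients not known to have died at the time of analysis will be censored at the time of last contact with study personnel" and survivors found by chart review would be cut back to an earlier contact. That requires chart review not to count as contact with study personnel. The documents do not say so, and section 11.6.2.11 lists chart review as a study assessment that includes survival. Last contact is close to the usual last-known-alive rule for OS. If Month 18 is a direct contact, the effect is zero for patients who attend it. At most, the OS wording is undefined.

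**Conclusion.** The PFS rule is wrong as written. It uses dates that carry no information on progression, and it biases the curve upward whenever contact outlasts a scheduled scan. The alternative-therapy rule has the same kind of defect, which was not sized separately.

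The sizes in the table rest on assumed dropout and contact patterns. The upper end needs patients who miss several consecutive scans while remaining reachable for many months. The median is unaffected at a true median of 4.6 months and sensitive at 4.1 months, which lies almost on the Cycle 6 scan date. Last-scan censoring recovers the full-scan curve here because stopping scans was assumed unrelated to progression; if it is related, neither rule is free of bias.

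Severity is minor to moderate. No error rate, sample size or dose decision depends on PFS. No OS bias is established.

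**What to change.** In section 14.3.10, replace both PFS censoring sentences with:

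> Patients without documented progression or death, including those lost to follow-up, starting alternative therapy, or event-free at the analysis, are censored for PFS at the date of the last evaluable tumour assessment (Day 1 if none).

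In the synopsis and section 8.1.2, state that telephone or chart review contributes to PFS only through documented progression or death and does not extend progression-free time. PFS should not simply be deleted from those sentences, because chart review can find progression documented outside study visits.

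Reconcile the synopsis, section 8.1.2 and section 11.6.2.12 on whether Months 15 and 18 run from Cycle 1 or from the end of Cycle 6, and on whether Month 18 is a visit with imaging.

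As a clarification only, define OS censoring as the date last known alive, by any source.

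The cost is a few sentences, with no extra patients or data. The reported PFS becomes slightly less favourable. Section 14.3.12 requires SAP approval before the Dose Expansion Cohort opens, which is a natural deadline.
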